7.3.4 Types of Surgery

Feasibility data show that OC/Surgicel is frequently used during general, vascular, gynecological, and oncological surgeries. A pilot clinical study of CELSTAT (Study 621101), conducted to provide sound relevant experience for planning the current study, supported cardiothoracic and general surgery. Therefore, general and vascular surgeries were chosen for this protocol. Excluded from this study are neurological, ophthalmological, urological, and gynecological surgery (except for gynecological surgery in postmenopausal women or surgery that results in removal of childbearing potential).

Minimally invasive surgery, as a distinct technique within each of the surgery types featured in this protocol, will not be allowed due to a potential significant bias resulting from, among others, differences in subject profile, technical demands, pre-and postoperative conduct, level of trauma and hemostasis achievement compared to the open surgery.

7.3.5 Primary Effectiveness Endpoint

TTH is the most meaningful criterion to assess the effectiveness of a hemostatic device. Timepoints were selected based on adequacy of demonstrating effectiveness of CELSTAT. In 3 nonclinical studies (Studies 53075, 52483, and 54201, summarized in the CELSTAT IB), the TTH after CELSTAT application was compared to commercially available hemostatic strip products (BloodSTOP or Surgicel Original); in all 3 studies, CELSTAT showed a statistically significantly shorter TTH than the comparator products. Other clinical studies use TTH between 3 minutes and 10 minutes after application of the device. A TTH of 5 minutes, which is supported by the pilot study, is a good compromise and applicable for all surgery types.

7.3.6 Statistical Considerations

Subgroup analyses in the pilot study showed that the surgery type seems to have high potential to influence the effectiveness results. Randomization will be stratified by surgery type in this study to control this effect. The sample size estimation is based on the assumption that the proportion of achieved hemostasis for the primary endpoint is █% for CELSTAT and █% for Surgicel.

The non-inferiority margin is defined as 10%. While the pilot study identified different rates of hemostasis at 5 minutes across surgery types, and surgery type had a high potential to influence effectiveness, a non-inferiority margin of 10% is still regarded as

appropriate, as the small-scaled pilot study may not provide adequate information allowing for a consistent judgement.

7.3.7 Relevant Literature and Data

Absorbable hemostatic adjuncts based on OC were first introduced into the market in the 1940s^{2,3} and devices based on oxidized regenerated cellulose were launched in 1960.⁴ OC offers superior handling characteristics when compared with gelatin foams. The knitted tissue strips can be cut to fit any size. The device does not stick to instruments and can easily be held firmly against the bleeding tissue until hemostasis is achieved.⁵ The device forms a lattice-like structure that traps platelets and contributes to clot formation by expanding and absorbing up to several times its own weight.⁶ Although the time to absorption of OC is thought to range from 2 to 6 weeks, depending on the amount used,⁷ there are reports describing histologic evidence of OC fibers several years after cardiac surgery.^{8,9,10}

Complications like allergic reactions, infections, granulomas and interference with bone healing have been noticed only rarely after the application of topical hemostatics.¹¹ Complications with the use of OC devices may arise from local swelling or possible inflammatory reactions.¹² Swelling of Surgicel in the proximity of the spinal cord or optic nerve has been linked to paralysis or nerve damage^{13,14} and it is therefore recommended to remove Surgicel after use in confined areas. Additionally, foreign body reactions have been reported after the use of OC devices.¹⁵

7.4 Anticipated Benefits and Risks of the Investigational Device and Clinical Investigation

Benefits

The use of CELSTAT as an adjunct to hemostasis offers the following benefits:

- CELSTAT is intended to serve as an adjunctive treatment to hemostasis similar to other OC devices. It offers a wide application range within the surgical area with currently only brisk (major) arterial bleeding as contraindication
- CELSTAT is a biodegradable material that can be left in situ, if used in accordance with instructions and general site practice, thus reducing the risk of recurrent bleeding, traumatization of the subject and disruption of the healing process

- Based on former and current animal data, CELSTAT is expected to be well tolerated. To date, no undesirable effects such as allergic reactions at the application site have been reported for CELSTAT
- CELSTAT is easy to use and requires no specific preparations before application. Based on its ease of use, effective hemostasis, and comparably low costs, CELSTAT may reduce the overall costs for therapy

Risks

Potential risks associated with the use of either CELSTAT or Surgicel include the following:

- Foreign body reaction
- Inflammatory reaction (including adhesive disease)
- Infection
- Rebleeding at the treated site (with or without removal of the device after achievement of hemostasis)
- Hematoma/seroma
- Thromboembolic hazards (blood clots)
- Compression-related problems (eg, stenosis, nerve damage, or sequelae related to decreased blood flow)

The study inclusion and exclusion criteria (see Section 10), and the study-specified device application procedures (see Section 9.8.1.3), have been developed to minimize the magnitude of these risks, while still allowing the study objectives to be met.

Conclusions

Considering that it is not planned to include surgery types with the highest of the associated risks and that the study device application procedures are designed to further mitigate these risks, and the previously noted potential benefits, the study is considered to be medically justified.

7.5 Compliance Statement

This study will be conducted in accordance with this CIP, the Declaration of Helsinki (as currently amended), Title 21 of the United States Code of Federal Regulations Parts 50, 54, 56, and 812, the International Conference on Harmonisation Guideline for Good

Clinical Practice (GCP) E6 (Apr 1996), GCP as laid down in ISO Norm 14155:2011, the European Union Medical Devices Directive 93/42/EEC as amended by Directive 2007/47/EC, MEDDEV 2.7/3 and MEDDEV 2.7/4 Guidelines on Medical Devices, and applicable national and local regulatory requirements.

8. OBJECTIVES OF THE CLINICAL INVESTIGATION

8.1 Primary Objective

The primary objective of the study is to assess the hemostatic effectiveness of CELSTAT in comparison to Surgicel, based on the achievement of hemostasis within 5 minutes after the start of treatment application (for a detailed definition see Section 9.4.1.1).

8.2 Secondary Objectives

The secondary objectives of the study are:

- To evaluate additional hemostatic effectiveness parameters of CELSTAT in comparison to Surgicel (for detailed definition, see Section 9.4.2.1)
- To evaluate the safety of CELSTAT (see Section 9.4.2.2)

9. STUDY DESIGN

9.1 Brief Summary

This is a prospective, randomized, controlled, single-blind pivotal trial of CELSTAT as an adjunct to hemostasis for the treatment of mild to moderate bleeding in subjects undergoing cardiothoracic, general and vascular surgery. The study is to evaluate the effectiveness and safety of CELSTAT vs active control in 258 subjects. It will be conducted at approximately 26 sites in the United States (20) and Europe (6).

9.2 Overall Study Design

This is a prospective, randomized, positive-controlled, subject-blinded, multicenter study.

Surgicel was chosen as comparator, as it is the standard among comparable marketed devices.

A total of 258 subjects scheduled for cardiothoracic, general and vascular surgery are planned to be randomized, at a 1:1 ratio to CELSTAT or Surgicel, in the study. Patients will be evaluated for eligibility at screening (Visit 1; in- or outpatient setting) within 14 days prior to the planned surgery. Final inclusion of subjects depends on the fulfillment of the intraoperative eligibility criterion. On the day of surgery (Visit 2;

Day 1), inclusion and exclusion criteria will be verified pre- and intraoperatively. The surgeon will be kept blinded to treatment assignment until after the TBS is selected.

The bleeding scale developed for use in the study in determining TBS inclusion suitability and response to study treatment is presented in the following table (Table 2).

Table 2. Bleeding Severity Scale

Grade	Visual Presentation	Anatomical Appearance	Qualitative Description	Visually Estimated Rate of Blood Loss (mL/min)
0	No bleeding	No bleeding	No bleeding	≤1.0
1	Ooze or intermittent flow	Capillary-like bleeding	Mild	>1.0-5.0
2	Continuous flow	Venule- and arteriolar-like bleeding	Moderate	>5.0-10.0
3	Controllable spurting and/or overwhelming flow	Non-central venous- or non-arterial-like bleeding	Severe	>10.0-50.0
4	Unidentified or inaccessible spurting or gush	Central arterial- or venous-like bleeding	Life threatening ^a	>50.0

^a Systemic resuscitation is required (eg, volume expanders, vasopressors, blood products).

Administration of the device is detailed in Section 9.8.1.3. Effectiveness and safety of the device will be assessed as described in Section 12.

Postoperative follow-up visits are scheduled for hospital discharge (or at Day 8 [±1] if the subject remains hospitalized for more than 1 week postsurgically; Visit 3); Day 31 (±5) (Visit 4); Day 61 (±10) (Visit 5); and Day 91 (±10) (Visit 6; end of study).

AEs and device related complications will be recorded from enrollment (time of signing of the informed consent form [ICF]) until the subject has completed participation in the study. Concomitant medication will be recorded from enrollment through the end of study participation. Safety laboratory assessments including coagulation parameters will be assessed at specified time points and the subject’s vital signs will be monitored. Intraoperative complications and intra- as well as postoperative rebleeding events will be documented.

An overview of the study design is presented in Supplement 21.1.

9.3 Duration of Study Period(s) and Subject Participation

The planned overall duration of the study is approximately 14 months from study initiation (ie, first subject's enrollment) to study completion (ie, last subject's last visit). The recruitment period is expected to be approximately 10 months.

The subject participation period is approximately 15 weeks from screening to subject completion (ie, last study visit), unless prematurely discontinued.

9.4 Outcome Measures

9.4.1 Primary Outcome Measures

9.4.1.1 Effectiveness

The primary effectiveness outcome measure is the proportion of subjects with hemostasis achieved at the TBS at 5 minutes after the start of application of the study device.

Hemostasis is defined as Grade 0 bleeding (no bleeding; see [Table 2](#) in Section 9.2) at the TBS after application of the randomized treatment, with no subsequent rebleeding at the TBS through surgical closure and no additional hemostatic treatment of another type after application of the randomized treatment.

9.4.1.2 Safety

The primary safety outcome measure is postoperative rebleeding from the TBS requiring surgical re-exploration during the subject's study participation.

9.4.2 Secondary Outcome Measures

9.4.2.1 Effectiveness

- TTH at the TBS within the 10-minute assessment period
- Proportions of subjects with hemostasis achieved at the TBS at 3, 7 and 10 minutes after the start of application of the study device
- Intraoperative rebleeding from the TBS after occurrence of hemostasis

9.4.2.2 Safety

- Occurrence of AEs/ADEs during the subject's study participation
- Clinical laboratory parameters
- Vital signs

9.5 Factors Influencing the Outcome

Surgery type (cardiothoracic, general and vascular) and bleeding severity (mild, moderate) may potentially influence hemostatic effectiveness. Therefore, these factors will be considered in the analysis.

9.6 Randomization and Blinding

9.6.1 Randomization

Subjects will be randomly assigned to CELSTAT or Surgicel at a ratio of 1:1. Randomization will be stratified by study center and surgery types (cardiothoracic, general, vascular surgery). It is aimed to achieve a similar distribution of the 3 surgery types in the randomized study population. This will be controlled via an interactive Web-response system (IWRS), [REDACTED] (USA), using dynamic allocation. Within [REDACTED], a capping strategy will be used to ensure equal allocation of randomized subjects across surgical types. On the day of surgery, upon confirmation of preoperative eligibility criteria, a member of the site study staff other than the surgeon will obtain a treatment assignment (CELSTAT or Surgicel) from the IWRS. To keep the surgeon blinded until an eligible TBS has been identified for study treatment, adequate amounts of each study product (CELSTAT and Surgicel) will be taken into the operating room for potential use of one of them as the study treatment.

Immediately after the subject's intraoperative eligibility for study treatment has been confirmed (ie, an eligible TBS with Grade 1 or 2 bleeding has been identified), the assigned treatment will be revealed to the surgeon and the assigned device will be applied to the TBS. Following surgery, the treatment assignment and the actual treatment applied will be entered in the electronic case report form (eCRF) for the subject.

If the subject's eligibility is not confirmed pre- or intraoperatively, the subject's operation will be performed according to hospital standards. The study site designee will enter the date and reason(s) for the subject's exclusion in the eCRF.

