Subjects eligible for randomization will present with an intraoperative TBS suitable for treatment with a hemostatic adjunct, after conventional surgical hemostasis has been completed. Male or female subjects of any ethnic group and race may be recruited.

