9.6.2 Blinding

This will be a single-blinded study. The subjects undergoing scheduled surgery will be blinded. In addition, the surgeon performing the surgery will remain blinded until an eligible TBS has been identified for study treatment (see Section 9.6.1). Otherwise, investigators, surgery personnel, site study personnel, CRO personnel and sponsor personnel will not be blinded.

[REDACTED]

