11. PROCEDURES

11.1 Informed Consent and Enrollment

Any subject who provides informed consent (ie, signs and dates the ICF, see Section 16.3) is considered enrolled in the study. Any subject who meets the inclusion criteria (including the intraoperative inclusion criterion) and does not fulfill the exclusion criteria is considered eligible for randomization. Screening failures are subjects who provide informed consent, but do not meet the eligibility criteria for treatment.

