21. SUPPLEMENTS

21.1 Study Flow Chart

Visit Number (Study Day)	Visit Type/Assessments
Visit 1 (Day -14 to -1)	Screening visit
	Assessment of inclusion and exclusion criteria
Visit 2 (Day 1)	Randomization and treatment visit (day of surgery)
	Preoperative: Confirmation of preoperative inclusion/randomization criteria; randomization
	Intraoperative: Identification of eligible target bleeding site; treatment application; assessment of hemostatic effectiveness and safety
Visit 3 (hospital discharge or Day 8 [\pm 1] if hospitalized longer than 1 week)	Hospital discharge visit
	Assessment of postoperative rebleeding and safety
Visit 4 (Day 31 [\pm 5])	Follow-up visit
	Assessment of postoperative rebleeding and safety
Visit 5 (Day 61 [\pm 10])	Follow-up visit
	Assessment of postoperative rebleeding and safety
Visit 6 (Day 91 [\pm 10] or at premature discontinuation)	End-of-study visit
	Assessment of postoperative rebleeding and safety

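### The protocol gives two moments of randomisation, so a patient with no eligible bleeding site is both randomised and a screening failure

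*Protocol*

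**What the plan says.** **Randomisation before the bleeding site is known.** Protocol Section 9.6.1 describes the draw as follows: "upon confirmation of preoperative eligibility criteria, a member of the site study staff other than the surgeon will obtain a treatment assignment". The surgeon learns the assignment only after an eligible TBS with Grade 1 or 2 bleeding has been found. The flow chart in 21.1 lists under Visit 2 "Preoperative: Confirmation of preoperative inclusion/randomization criteria; randomization", and puts identification of the TBS in the later, intraoperative step.

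**Randomisation after the bleeding site is known.** Section 11.1 states: "Any subject who meets the inclusion criteria (including the intraoperative inclusion criterion) and does not fulfill the exclusion criteria is considered eligible for randomization". Section 7.2 (background) has the same sense: "Subjects eligible for randomization will present with an intraoperative TBS suitable for treatment with a hemostatic adjunct". A data item in the Section 12.2 recording list also places conventional measures at the TBS before randomisation.

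**Status of a patient with no eligible TBS.** Section 11.1: "Screening failures are subjects who provide informed consent, but do not meet the eligibility criteria for treatment". Section 9.2 makes final inclusion depend on the intraoperative criterion. The last paragraph of 9.6.1 has such a patient operated on by hospital standards, and "The study site designee will enter the date and reason(s) for the subject's exclusion in the eCRF".

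**What hangs on being randomised.** Section 10 sets 258 randomised patients, 129 per group. In 9.6.1, "a capping strategy will be used to ensure equal allocation of randomized subjects across surgical types". Section 13.2 puts every randomised patient in the FAS, defines the per-protocol set (PPS) as a subset of it, and removes patients who fail eligibility criteria from the PPS only.

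**The concern.** The two rules cannot both hold. Under 9.6.1 and 21.1 every patient is randomised before satisfying what 11.1 requires for randomisation. For most patients this is harmless, because a TBS is found and the device is applied. It matters for a patient who is assigned and then has no eligible TBS.

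Three things depend on how that patient is classed:

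- **The FAS and the 13.3 sensitivity analyses.** The patient has no 5-minute outcome. The first sensitivity analysis scores missing data as failure. The worst-case analysis scores them as failure on CELSTAT and success on Surgicel. Either way, an untreated patient is scored as evidence about a device.
- **The 258 and the surgery-type caps.** If assigned but untreated patients count, enrolment could stop, or a surgery type could close, with fewer treated patients than intended. A later analysis plan can redefine the FAS but cannot reverse enrolment that has already closed.
- **The size of the PPS.** These patients drop out of it, and the primary analysis and its power rest on the PPS.

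**Working it through.** **1. The textual check**

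Take a patient assigned by the IWRS preoperatively in whom no Grade 1 or 2 TBS is found.

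| Section | Status of this patient |
|---|---|
| 9.6.1 (assignment), 21.1 | Randomised |
| 10 (the 258), 9.6.1 (caps), 13.2 (FAS) | Counted, if randomised is read literally |
| 13.3 (sensitivity analyses on the FAS) | Failure; worst case: CELSTAT failure or Surgicel success |
| 9.2 | Not finally included |
| 9.6.1 (last paragraph) | Excluded |
| 11.1 | Not eligible for randomisation; screening failure |

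No section says that an unrevealed assignment is not a randomisation, or that it is released from the 258 or the caps.

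**2. Reproducing the plan's figure (13.1)**

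Inputs: 121 evaluable per group, PPS 5% smaller than the number randomised, three equal surgery types.

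- 121 / 0.95 = 127.4, so 128. Rounded up to a multiple of 3 this is 129 per group, or 258 in total. The plan's figure reproduces.
- The 121 itself cannot be recomputed, because both planning rates are redacted.

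**3. How much loss the plan tolerates**

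- 129 − 121 = 8 per arm, and 8 / 129 = 6.2%.
- The limit is per arm. Sixteen losses over both arms are safe only if they split 8 and 8. If 16 losses fall at random, one arm is below 121 about 80% of the time.
- Section 13.1 sets the 5% as the whole gap between randomised and PPS. Under 9.6.1 it must cover no-TBS patients and every other PPS exclusion together.

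**4. Power if no-TBS patients count towards the 258 (illustration only)**

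The no-TBS share f is not given. With f as the only loss:

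- n per arm = 129 × (1 − f)
- power = Φ( (pC − pS + 0.10) / √[(pC(1−pC) + pS(1−pS)) / n] − 1.96 )

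The assumed pairs (pC, pS) are (0.916, 0.916), (0.90, 0.89), (0.86, 0.83) and (0.80, 0.75). At n = 121 they give 80.1%, 79.7%, 79.9% and 79.9%, in line with the stated 80%. The pilot rates in 7.3.2 (51/55 and 24/27) give 96.2%.

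Worked case, pair (0.90, 0.89), f = 10%: n = 116.1; variance sum 0.0900 + 0.0979 = 0.1879; standard error √(0.1879 / 116.1) = 0.0402; 0.11 / 0.0402 − 1.96 = 0.774 (unrounded standard error); Φ = 78.1%.

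| f | n per arm | Power, assumed pairs | Power, pilot rates |
|---|---|---|---|
| 5% | 122.6 | 80.2–80.6% | 96.4% |
| 10% | 116.1 | 78.1–78.4% | 95.5% |
| 20% | 103.2 | 73.2–73.6% | 93.2% |
| 30% | 90.3 | 67.4–67.8% | 89.7% |

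If only patients with a confirmed TBS count as randomised, as 11.1 implies, f = 0 and the 129 per group stands.

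**The case against.** The strongest reply is that little of consequence follows, and most of that reply stands.

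- **The primary comparison.** A reader might infer that the primary result is biased. The protocol does not support that. The surgeon is to stay blinded until the TBS is selected, so finding no TBS should not depend on the assigned arm, and the primary analysis is on the PPS, which excludes these patients.
- **The FAS.** Section 13.4.1 makes it supportive. The main rule in 13.3 uses available data only, so a patient with no outcome is already left out of the main FAS analysis. The two sensitivity analyses have no decision rule, so a pass rate computed for them would not be the power of any planned test.
- **Power.** A reader might infer that the trial is underpowered. Nothing in the protocol says f is large. All 82 patients enrolled in the pilot had a hemostasis outcome at a primary TBS, although the protocol does not say how enrolment was defined there. Adding a further 5% loss on top of f would also be wrong, because 13.1 defines the 5% as the whole gap.
- **The IWRS.** A reader might infer that the system will fill the 258 and the caps with untreated patients. The protocol does not say whether unused assignments are counted or released. This is a risk, not a shown outcome.

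One could also read randomised as meaning that the assignment has been revealed. That would resolve the conflict, but no section says so, and 21.1 names randomisation as part of the preoperative step.

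**Conclusion.** The protocol is wrong as written and should be corrected. The contradiction between 9.6.1 with 21.1 and 11.1 is in the text and needs no assumption. More than detail is missing: followed literally, 13.2 and 13.3 score patients who received no device.

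The size is bounded. The plan tolerates 8 PPS losses per arm (6.2%). A 5% no-TBS share with no other loss leaves 122.6 per arm and causes no shortfall. Larger shares would cost power, to about 78%, 73% and 68% at 10%, 20% and 30%. Those figures rest on an assumed f, on assumed rates that yield about 80% at 121 per arm, and on untreated patients counting towards the 258. At the pilot rates, power stays at 89.7% or more.

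The absence of bias in the primary PPS comparison depends on the surgeon being blinded until the TBS is chosen.

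**What to change.** Define one moment at which a patient counts as randomised, and align Sections 9.6.1, 11.1, 13.2, 13.3 and 21.1 with it, together with the wording in 7.2 and 12.2.

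**Cheaper version.** Keep the concealed preoperative IWRS call. Count towards the FAS, the 258, the caps and the 13.3 imputation only patients whose eligible TBS was confirmed and recorded before the assignment was revealed. Report all others as screening failures by assigned arm, as a check on balance.

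Its costs are:
- The FAS becomes a modified one and relies on concealment until the TBS is confirmed. Section 9.6.2 says of everyone except the patient and, until that point, the surgeon: "Otherwise, investigators, surgery personnel, site study personnel, CRO personnel and sponsor personnel will not be blinded".
- TBS status must be reported back to the IWRS, with a rule for whether unused assignments stay in the dynamic allocation. This is more than a wording change.

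**Alternative.** Make the IWRS call only after the TBS is confirmed, as 11.1 implies. This removes the reliance on concealment, but adds an intraoperative web call at the point where 9.6.1 wants treatment to start at once.

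Neither version needs more treated patients than the planned 258.
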